11.1.2.3 Best overall RECIST response (BoR)

Best overall RECIST response (BoR) is calculated based on the overall visit responses from each RECIST assessment, described in Appendix G. It is the best response a patient has had following randomisation but prior to starting any subsequent cancer therapy and prior to RECIST progression or the last evaluable assessment in the absence of RECIST progression.

Categorisation of best overall response will be determined programmatically based on the RECIST 1.1 criteria (Appendix G) for the BICR data, using the following response categories: complete response (CR), partial response (PR), stable disease (SD) and progressive disease (PD).

Best overall response will be determined programmatically from the time point response using BICR data. In addition, this will also be reported using investigator-recorded assessment.

For determination of a best response of SD, the earliest of the dates contributing towards a particular overall visit assessment will be used. SD should be recorded at least 6 weeks +/- 1 week, i.e. at least 35 days (to allow for the assessment window), after randomisation. For CR/PR, the initial overall visit assessment which showed a response will use the latest of the dates contributing towards a particular overall visit assessment.

For patients whose disease progression event is death, BoR will be calculated based on data up until the last evaluable RECIST assessment prior to death.

For patients who die with no evaluable RECIST assessments, if the death occurred ≤ 13 weeks (i.e. 12 weeks ± 1 week) after randomisation then BoR will be assigned to the progression (PD) category. For patients who die with no evaluable RECIST assessments, if the death occurred > 13 weeks (i.e. 12 weeks ± 1 week) after randomisation then BoR will be assigned to the non-evaluable (NE) category.

Progression events that have been censored due to them being more than two missed visits after the last evaluable assessment will not contribute to the BoR derivation.

A patient will be classified as a responder if the RECIST criteria for a CR or PR are satisfied at any time up to and including the defined analysis cut-off point. For each treatment group, the objective response rate (ORR) is the number patients with a CR and PR divided by the number of patients in the treatment group in the evaluable for response (EFR) analysis set.

Only patients with measurable disease at enrolment can achieve an objective response of CR or PR.

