6.3.2 Tumour Evaluation

RECIST 1.1 criteria will be used to assess patient response to treatment by determining progression free survival (PFS) times (the RECIST 1.1 guidelines for measurable, non-measurable, target and non-target lesions and the objective tumour response criteria (complete response, partial response, stable disease or progression of disease) are presented in Appendix G.).

Categorisation of objective tumour response assessment will be based on the RECIST criteria of response: complete response (CR), partial response (PR), stable disease (SD), progression of disease (PD) and not evaluable (NE). Target lesion (TL) progression will be calculated in comparison to when the tumour burden was at a minimum (i.e. smallest sum of diameters previously recorded on study). In the absence of a best response of progression, tumour response (CR, PR, SD) will be calculated in comparison to the baseline tumour measurements obtained before randomisation.

For patients with non-measurable disease only at baseline, categorisation of objective tumour response assessment will be based on the RECIST criteria of response: CR (complete response), PD (progression of disease) and Non CR/Non PD.

If the investigator is in doubt as to whether disease progression has occurred, particularly with response to NTL (non-target lesion) or the appearance of a new lesion, it is advisable to continue treatment until the next scheduled assessment or sooner if clinically indicated and reassess the patient's status. If repeat scans confirm disease progression, then the date of the initial scan should be declared as the date of disease progression.

To achieve 'unequivocal progression' on the basis of non-target disease, there must be an overall level of substantial worsening in non-target disease such that, even in presence of SD or PR in target disease, the overall tumour burden has increased sufficiently to merit discontinuation of therapy. A modest increase in the size of one or more non-target lesions is usually not sufficient to qualify for unequivocal progression status.

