12.1.4 PK Analysis set

PK data will be analysed according to treatment received. This population will comprise all patients who receive study treatment as per protocol (PP) and do not violate or deviate from the protocol in ways that would significantly affect the PK analyses. The population will be defined by the Study Team Physician, Pharmacokineticist and Statistician prior to any analyses being performed.

Table 9 Summary of Outcome Variables and Analysis Populations

Outcome Variable	Populations
Efficacy Data	
- PFS	FAS (ITT)
- OS, PFS2, objective response rate, symptom/QoL endpoints	FAS (ITT)
Demography	FAS (ITT)
Pharmacokinetic data	PK
Safety Data	
- Exposure	Safety
- Adverse Events	Safety
- Lab measurements	Safety
- Vital Signs	Safety

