12.2.3.3 Summary of Best overall RECIST Response (BoR) and ORR

For each treatment arm, best overall response (BoR) will be summarised by n (%) for each category (CR, PR, SD, PD, NE). No formal statistical analyses are planned.

The objective response rate (ORR) will be summarised (i.e., number of patients (%)) by treatment group.

ORR and BOR will be presented based on the BICR data and also the investigator recorded data.

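### Objective response rate has two denominators and two observation windows in the protocol, so the reported rate depends on which section is followed

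*Protocol*

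**What the plan says.** **Numerator.** Protocol section 11.1.2.3 defines best overall response (BoR) as the best response after randomisation "but prior to starting any subsequent cancer therapy and prior to RECIST progression", or up to the last evaluable assessment if there is no progression. Later in the same section comes the responder rule: "A patient will be classified as a responder if the RECIST criteria for a CR or PR are satisfied at any time", with the analysis cut-off as its only stated limit.

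**Denominator.** Section 11.1.2.3 divides responders by the patients in the evaluable-for-response (EFR) set. Section 12.1.3 defines EFR as the randomised patients with measurable disease at baseline, and Table 10 in section 12.2 also divides by patients with measurable disease. Table 9, printed under section 12.1.4, lists "OS, PFS2, objective response rate, symptom/QoL endpoints" against the FAS and has no EFR row. Section 12.1.1 puts all efficacy data on the FAS and makes no exception for ORR.

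**Status.** ORR is a secondary endpoint. Table 10 calls it descriptive only, and section 12.2.3.3 says "No formal statistical analyses are planned".

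**The concern.** Both conflicts lie within the protocol's current text; neither is detail left to the SAP.

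Inclusion criterion 9 in section 4.1 admits patients whose only disease is non-measurable, so EFR is smaller than the FAS by design. The same scans then yield two different ORRs, depending on the section followed.

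On the numerator, sections 3.1 and 6.3.1 keep RECIST scans going until objective progression, whatever the treatment decisions. A patient can therefore start another drug and still be scanned. If CR or PR first appears on that drug, the BoR rule ignores it and the responder rule counts it. The patient would be stable disease in the BoR table and a responder in the ORR table, and the later drug's effect would be credited to the randomised arm.

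The trial is open label, so window and population should be settled in the text and not chosen once data are in view.

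**Working it through.** The protocol states no expected ORR and no expected share of patients with measurable disease, so there is no ORR figure to reproduce. The check compares the rules and sizes their effect under labelled assumptions.

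**Inputs**
- About 310 patients randomised 2:1 (section 3.1): 310 × 2/3 ≈ 207 olaparib and 310 × 1/3 ≈ 103 chemotherapy.
- Share with measurable disease: not given. Assumed 70–90%.
- EFR-based ORR: not given. 20% and 40% are assumed for illustration. Section 1.1.6.1 reports 41% and 22% at two doses in one phase II breast cancer study, and lower rates in other olaparib studies.

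**Step 1: denominator.** Section 11.1.2.3 also says "Only patients with measurable disease at enrolment can achieve an objective response of CR or PR", so moving from EFR to FAS enlarges the denominator and leaves the numerator alone:

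FAS rate = responders / FAS = EFR rate × (EFR / FAS)

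For the olaparib arm (FAS 207), in whole patients:

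| Measurable share | EFR n | EFR rate near 40% | same responders on FAS | EFR rate near 20% | same responders on FAS |
|---|---|---|---|---|---|
| 70% | 145 | 58/145 = 40.0% | 58/207 = 28.0% | 29/145 = 20.0% | 29/207 = 14.0% |
| 80% | 166 | 66/166 = 39.8% | 66/207 = 31.9% | 33/166 = 19.9% | 33/207 = 15.9% |
| 90% | 186 | 74/186 = 39.8% | 74/207 = 35.7% | 37/186 = 19.9% | 37/207 = 17.9% |

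Randomisation makes the measurable share similar in both arms in expectation, although it is not a stratification factor. The factor EFR/FAS then roughly cancels in the ratio of the two response rates. The difference in percentage points shrinks by that same factor.

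**Step 2: who can fall between the two numerator rules.** Three conditions are needed:
1. The patient starts a subsequent cancer therapy.
2. There is no BICR-confirmed progression at that point, so scans continue. Section 3.1 provides for patients who change therapy before progression. It also allows an investigator call of progression that central review does not confirm, with a further scan requested at the next RECIST visit, while treatment follows the site's reading.
3. CR or PR against the original baseline is first met on a later scan.

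Table 1, footnote g, stops RECIST assessments after progression, and sections 3.1 and 6.2.6 end central review at the primary PFS analysis. The route is open but narrow.

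**Step 3: size per patient.** One extra responder adds 1/EFR to the rate.
- Control, 70% measurable: 103 × 0.7 ≈ 72; 1/72 = 1.4 points.
- Control, 80% measurable: 103 × 0.8 ≈ 82; 1/82 = 1.2 points.
- Control, 90% measurable: 103 × 0.9 ≈ 93; 1/93 = 1.1 points.
- Olaparib, 70–90% measurable: 1/145 = 0.7 down to 1/186 = 0.5 points.

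With 2:1 allocation, one such patient moves the control rate about twice as far as the olaparib rate. The documents give no basis for the number of such patients.

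**The case against.** On the denominator, the passages that define ORR agree. Section 11.1.2.3 names EFR, Table 10 says measurable disease, and section 12.1.3 sets EFR up separately for central and investigator data. Table 9 and section 12.1.1 are general statements, and a careful analyst would follow the specific definition. That makes EFR the likely intention, and it is why the fix below keeps EFR. It does not remove the conflict: Table 9 names ORR explicitly and assigns it to the FAS.

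On the numerator, the responder sentence sits in the BoR section, whose opening sets the window, so responder may simply mean BoR of CR or PR. That reading is natural, but the sentence names a different end point, the analysis cut-off, and nothing ties it back to the BoR window.

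Several stronger readings are tempting, and the documents do not support them:
- *Every response after a change of therapy would be counted.* Scans stop at progression, so only patients who switch without BICR-confirmed progression are exposed.
- *The control rate could be inflated by many points.* That needs an assumed number of late responders, for which the protocol gives no source.
- *The measurable-disease rule corrupts ORR.* Section 6.3.2 ("For patients with non-measurable disease only at baseline, categorisation of objective tumour response assessment will be based on the RECIST criteria") and Appendix G Table 4 allow CR without target lesions, against the limit in section 11.1.2.3. On the EFR set these patients are in neither numerator nor denominator, so at most a cell of the BoR table changes.
- *A formal comparison is missing.* Secondary objective 1 speaks of comparing efficacy, but the synopsis, Table 10 and section 12.2.3.3 consistently make ORR descriptive. A stratified odds ratio would be a preference, not the correction of an error.

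**Conclusion.** The point holds as an inconsistency in a named secondary endpoint. The denominator conflict is the firmer part. Under an assumed measurable share of 70–90%, an assumed EFR rate of 40% would be reported as about 28–36% on the FAS. This changes each arm's absolute rate and leaves the ratio between arms roughly as it was.

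The numerator conflict is real as written but limited in reach. The number of patients affected is unknown and probably small. Each would add about 1.2–1.4 points to the control rate if 72–82 of about 103 controls are evaluable, which rests on an assumed share of 70–80%.

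A reader might infer that the trial's efficacy conclusion is at risk. It is not: ORR is descriptive and outside the multiple testing procedure of section 12.2.1, so the primary PFS analysis and the type I error are unaffected. The text should be corrected, but this is not a flaw in the design.

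**What to change.** 1. In section 11.1.2.3, replace the open-ended responder rule: a responder is a patient whose BoR is CR or PR, that is, a response before RECIST progression and before any subsequent cancer therapy. BoR and ORR then share one window.
2. In Table 9, give ORR its own row with the EFR set as population. In section 12.1.1, except ORR from the statement that all efficacy data use the FAS. Section 11.1.2.3 and Table 10 already agree with this.

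The cost is a few lines of wording, with no new data and no change to PFS, PFS2 or OS. The downside is that ORR may be slightly lower than under the any-time rule. A sentence stating how CR in patients without measurable disease appears in the BoR table would be a useful tidy-up, and an estimate of the treatment difference in ORR is optional. Neither is needed to remove the inconsistency.

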11.2 Calculation or derivation of safety variable(s)

Safety and tolerability will be assessed in terms of AEs, physical examination, laboratory data including clinical chemistry and haematology, vital signs including blood pressure(BP), pulse and ECG. These will be collected for all patients. Appropriate summaries of these data will be presented.

11.2.1 Other significant adverse events (OAE)

During the evaluation of the AE data, an AstraZeneca medically qualified expert will review the list of AEs that were not reported as SAEs and DAEs. Based on the expert's judgement, significant adverse events of particular clinical importance may, after consultation with the Global Patient Safety Physician, be considered OAEs and reported as such in the Clinical Study Report. A similar review of laboratory/vital signs/ECG data will be performed for identification of OAEs.

Examples of these are marked haematological and other laboratory abnormalities, and certain events that lead to intervention (other than those already classified as serious), dose reduction or significant additional treatment.

11.3 Calculation or derivation of patient reported outcome variables

All items/questionnaires will be scored according to published scoring guidelines or the developer's guidelines, if published guidelines are not available.

EORTC-QLQC30

The EORTC QLQ-C30 will be scored according to the EORTC scoring manual ([Fayers et al 1999](#)). Each scale will be transformed to a 100-point scale as per the manual.

Mean change from baseline in health related quality of life (HRQoL) will be assessed using the EORTC QLQ-C30 global QoL scale which includes two items from the QLQ-C30: "How would you rate your overall health during the past week? (Item 29) and "How would you rate your overall quality of life during the past week? (Item 30).

HRQoL Visit responses

A change of at least 10 points in the global QoL score will be considered as a clinically relevant or a minimally important difference ([Osoba D et al 1998](#)).

A visit response of "deterioration" will be defined as a decrease of 10 points or more or where "Subject too heavily affected by symptoms of disease under investigation" is answered as the reason for not completing HRQoL at visit.

Table 7 Visit response in Health Related QoL

Score	Change from baseline	Visit response
EORTC QLQ-C30 Global QoL score	$\geq +10$	Improved
	≤ -10 or “Subject too heavily affected by symptoms of disease under investigation” is answered as the reason for not completing HRQoL at visit	Deterioration
	Otherwise	No change
EORTC QLQ-C30 functional scales: physical, role, emotional, cognitive and social	$\geq +10$	Improved
	≤ -10 or “Subject too heavily affected by symptoms of disease under investigation” is answered as the reason for not completing HRQoL at visit	Deterioration
	Otherwise	No change

A patient’s best overall QoL response will be derived as the best QoL response the patient achieved, based on evaluable QoL data collected from randomisation up to the earliest of starting any subsequent cancer therapy or death. The criteria in [Table 8](#) will be used to assign a best QoL response for HRQoL based on the 2-item global QoL score.

Table 8 Best response in QLQ-C30 scores: FAS population

Overall Score Response	Criteria
Improved	Two visit responses of “improved” a minimum of 21 days apart without an intervening visit response of “deterioration”
No Change	Does not qualify for overall score response of “improved”. Two visit responses of either “no change” or “improved” and “no change” a minimum of 21 days apart without an intervening visit response of “deterioration”
Deterioration	Does not qualify for overall score response of “improved”. A visit response of “deterioration” without response of “improved” or “no change” within 21 days.
Other	Does not qualify for one of the above.

Change must be sustained for at least 21 days (i.e. there must be no response of “improved” or “no change” within 21 days of the visit response of “deterioration”).

For each subscale, if less than 50% of the subscale items are missing, then the subscale score will be divided by the number of non-missing items and multiplied by the total number of

items on the subscales (Fayers et al 1999). If at least 50% of the items are missing, then that subscale will be treated as missing. Missing single items are treated as missing. The reason for any missing questionnaire will be identified and recorded. If there is evidence that the missing data are systematic, missing values will be handled to ensure that any possible bias is minimised.

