Patients with unknown *BRCA* status must consent to provide 2 blood samples for germline *BRCA* testing and follow all local ethical procedures for such genetic testing. One sample will be used to test for *BRCA* mutations using the current commercial Myriad *BRCA* analysis test prior to study entry. The second blood sample from all tested patients (including those who do not have a *BRCA* mutation) is required for a bridging study to validate the companion diagnostic test for olaparib and/or assessment of current and future *BRCA* mutation assay(s). When the result from the Myriad test indicates the patient does have a deleterious or suspected deleterious germline *BRCA* mutation and the patient meets all other eligibility criteria, the patient can be randomised into the study.

After confirmation of eligibility patients will be randomised 2:1 to receive either:

- Arm A; olaparib 300 mg po twice daily
- Arm B; Physicians choice of chemotherapy (capecitabine, vinorelbine or eribulin)

Following randomisation patients in both treatment arms will attend clinic visits weekly for the first 3 weeks of treatment (Days 1, 8 and 15). Patients will then attend clinic visits every 3 weeks while receiving study treatment. Patients should continue to receive study treatment until objective radiological disease progression as per RECIST as assessed by the investigator,

unacceptable toxicity or as long as they do not meet any other discontinuation criteria as outlined in Section 5.8.

Patients will have RECIST assessments until evidence of objective disease progression irrespective of treatment decisions (i.e even if they discontinue study treatment and/or receive a subsequent therapy prior to progression). RECIST assessments will be scheduled every 6 weeks (+/- 1 week) from randomisation for the first 24 weeks and then every 12 weeks (+/- 1 week) thereafter.

All CT/MRI scans will be sent to an AstraZeneca appointed Clinical Research Organisation (CRO) for blinded independent central review. All treatment decisions will be based on site assessment of scans. Patients who are determined to have progressed according to RECIST 1.1 criteria by the Investigator will have scans centrally reviewed for confirmation of objective disease progression. If disease progression is not confirmed at central review an additional RECIST assessment will be requested at the next scheduled RECIST visit.

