- i Urinalysis should be performed at screening. After screening, urinalysis will only be required if clinically indicated
- j In the event of suspected pregnancy during the study, the test should be repeated and, if positive, the patient discontinued from study treatment immediately.
- k Any patient who consents to study related Myriad *gBRCA* status testing, must also have a blood sample taken at the same time for the purpose of developing and validating a future diagnostic test(s) for *BRCA* mutations
- l Samples to be taken on Day1 only for patients with known *BRCA* mutation who have not completed PART 1 screening
- m Adverse events must be captured from time of consent. However, in Screening PART 1 of the study only SAEs related to study procedures will be collected.
- n EORTC QLQ-C30 questionnaires to be completed every 6 weeks until disease progression.
- o Healthcare Resource Use should be collected up to disease progression or treatment discontinuation (and 30 day follow-up), whichever is the latter.
- p Optional tumour biopsies to be taken during screening and at disease progression. Sample will only be submitted to the study biobank once the patient has been randomised.
- q Mandatory blood samples to be taken prior to dosing on Day 1 and at disease progression
- r Details of all anti-cancer treatments (including, but not limited to, chemotherapy and targeted agents) post discontinuation of study treatment need to be recorded
- s In addition to their regular 8 weekly contact, patients will be contacted in the 7 days following a specified date (data cut off date) for each survival analysis. The status of ongoing, withdrawn (from the study) and “lost to follow-up” patients at the time of an overall survival analysis should be obtained by the site personnel by checking the patients notes, hospital records, contacting the patients general practitioner and checking publicly available death registries. In the event that the patient has actively withdrawn consent to the processing of their personal data the vital status of the patient can be obtained by site personnel from publicly available resources where it is possible to do so under applicable local laws (see section 5.9).

-
- ^t Sample will only be submitted to the study biobank once the patient has been randomised.

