6.5.3 Administration of PRO questionnaires

Paper-based EORTC QLQ-C30 will be administered at baseline (prior to randomisation once eligibility is confirmed), and then every 6 weeks until disease progression.

Paper-based CTSQ will be administered every six weeks and at discontinuation of study treatment.

Each centre must allocate the responsibility for the administration of the questionnaires to a specific individual (e.g., a research nurse, study coordinator) and if possible assign a back-up person to cover if that individual is absent. The AZ Study Delivery Team (or delegate) will provide relevant training in administration of the questionnaires. The significance and relevance of the data need to be explained carefully to participating patients so that they are motivated to comply with data collection.

The instructions for completion of the PRO questionnaires are as follows:

- The EORTC QLQ-C30 should be completed before the CTSQ.
- They must be completed prior to any other study procedures (following informed consent) and before discussion of disease progress to avoid biasing the patient's responses to the questions. They must be completed in private by the patient
- The patient should be given sufficient time to complete at their own speed
- The patient should not receive help from relatives, friends or clinic staff to answer the questionnaire.
- On completion of the questionnaire it should be handed back to the person responsible for questionnaires who should check for completeness
- Only one answer should be recorded for each question

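### Table 8's 21-day test of sustained QoL deterioration has no effect with 6-weekly questionnaires, so one bad visit counts as sustained

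*Protocol*

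**What the plan says.** **Schedule.** Protocol section 6.5.3 gives the QLQ-C30 at baseline "and then every 6 weeks until disease progression". The footnote to Table 1 in section 3.1 agrees: "EORTC QLQ-C30 questionnaires to be completed every 6 weeks until disease progression". Table 1 marks no QLQ-C30 at the treatment discontinuation visit; only the CTSQ-16 is marked there.

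**Classification.** Table 8 in section 11.3 sorts patients into Improved, No change, Deterioration and Other.
- Improved needs two improved visits "a minimum of 21 days apart without an intervening visit response of" deterioration.
- No change asks for "Two visit responses of either “no change” or “improved” and “no change” a minimum of 21 days apart", again with no deterioration between them.
- Deterioration asks for "A visit response of “deterioration” without response of “improved” or “no change” within 21 days". It also excludes patients who qualify as Improved, but it does not mention those who qualify as No change.

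**The sustained rule.** Below the table stands "Change must be sustained for at least 21 days", explained as meaning that "there must be no response of “improved” or “no change” within 21 days of the visit response of “deterioration".

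**Order.** The text just above Table 8 defines a patient's overall QoL response as the best one reached.

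**Use.** Section 12.2.3.4 presents best overall response by arm for the global score and the five functional scales. For the global score it includes only patients with a baseline of at least 10.

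**The concern.** The rule can reject a deterioration only if a better response is recorded within 21 days of it. If questionnaires are never that close together, the rule rejects nothing and the word sustained describes a property that was not checked. A patient who dips once and recovers at the next visit would be reported as having sustained deterioration.

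The rows also demand different amounts of evidence: two visits for Improved and for No change, one for Deterioration. What is at stake is how a by-arm descriptive table in an open-label trial is read. Some of its Deterioration entries would be single-visit fluctuation under a label that says otherwise.

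**Working it through.** The plan gives no figure of its own to reproduce here. The check has three steps.

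**1. Can the 21-day test bind?** Inputs: a 6-week interval (section 6.5.3), the ±3-day window for on-treatment visits (Table 1), and, as a worst case, the widest window given for any 6-weekly assessment: "RECIST assessments will be scheduled every 6 weeks (+/- 1 week) from randomisation for the first 24 weeks".

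Smallest gap between consecutive questionnaires = 42 − 2 × window.
- No window: 42 − 0 = 42 days
- ±3 days: 42 − 6 = 36 days
- ±7 days: 42 − 14 = 28 days

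All exceed 21 days. For the test to bind, two neighbouring questionnaires would have to move towards each other by 42 − 21 = 21 days in total, or an unplanned one would have to be completed.

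**2. What does Table 8 then do?** Every possible sequence of visit responses (I = improved, N = no change, D = deterioration) for one to six post-baseline visits was classified by the literal rows. These are counts of sequences, not patient probabilities.
- Six visits: 3^6 = 729 sequences containing 729 × 6 / 3 = 1,458 deterioration visits. The 21-day test fails for 0 of the 1,458 at gaps of 42, 36 and 28 days. At a 21-day gap it would fail for 1,188.
- Three visits: 27 sequences, of which 19 contain a D. Two of these are Improved (IID, DII). Six meet both the No change and Deterioration rows (NND, DNN, IND, NID, DIN, DNI), and taking the best response makes them No change. That leaves 19 − 2 − 6 = 11 labelled Deterioration: DDD, DDN, DDI, NDD, IDD, DND, DID, NDN, NDI, IDN, IDI.
- In the last four of those 11 (NDN, NDI, IDN, IDI) the only deterioration is followed by a better response at the very next visit. A patient whose single questionnaire is D also qualifies.
- With six visits, 285 of 729 sequences meet both rows and become No change. Of the 85 that stay Deterioration, 8 contain no D that is either repeated at the next visit or recorded at the last one.

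**3. How often might this matter?** The protocol gives no variability figures, so these are assumptions: no true change, baseline mean 63, between-patient SD 22, within-patient SD 8 to 16, and baseline score at least 10. The global score has two items scored 1 to 7, so it moves in steps of 100/12 = 8.33, and a change of 10 or more needs two steps (16.67). With the best response taken, simulation gives the following percentages labelled Deterioration.

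| Post-baseline visits | Table 8 as written | Two consecutive deteriorations required |
|---|---|---|
| 3 | 16% to 34% | 7% to 19% |
| 5 | 7% to 20% | 6% to 17% |

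The ranges run from within-patient SD 8 to 16.

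**The case against.** The strongest reply is that little depends on this table. The main HRQoL analysis is the mixed model of change in the global score (Table 10, section 12.2.3.4), which does not use Table 8. The multiple testing procedure in section 12.2.1 covers only PFS, PFS2 and OS. Best response carries no test. All of this stands and limits the point to a minor one.

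It is also fair that an off-schedule questionnaire could trigger the 21-day test. The claim is therefore that the test never binds on schedule, not that it can never bind at all.

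Three stronger readings are tempting, and the documents do not support them.
- *The overlap of No change and Deterioration leaves the table undefined.* The rows do overlap, as in no change, no change, deterioration. But the best-response definition just above the table ranks No change higher, so every sequence gets one label. The missing exclusion is a wording gap only.
- *Half the patients could be falsely labelled.* Rates of 28% to 55% arise only if patients who also meet No change are counted as deteriorated, contrary to the best-response definition.
- *More visits give noise more chances, so the arm with longer follow-up looks worse.* With the best response taken, more visits give more chances to reach No change or Improved. At within-patient SD 12 the noise-only rate falls: 34%, 26%, 18% and 15% at 2, 3, 4 and 5 visits.

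A last objection concerns the remedy. Questionnaires stop at progression, so a strict two-visit rule would send a patient whose first fall is at the last questionnaire to Other, and would do so more often where progression is early. That is a good reason not to adopt a strict two-visit rule.

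**Conclusion.** Wrong as written, minor. The protocol states that deterioration must be sustained and then sets a test that 6-weekly questionnaires inside any window it gives cannot fail. This follows from the schedule alone and needs no assumption about the data. One deterioration visit is enough, including when the patient has recovered at the next.

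The size does rest on the assumed means and SDs. The excess of labelled deteriorations over a two-consecutive-visit rule is material with three post-baseline questionnaires and small with five. The defect affects what the Deterioration category means in a descriptive table. It does not touch the MMRM, the multiple testing procedure or any efficacy conclusion.

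**What to change.** - In the Deterioration row of Table 8, replace the condition on responses within 21 days by: *not followed by improved or no change at the next scheduled 6-weekly questionnaire*.
- State that a deterioration at the last available questionnaire counts as Deterioration and is shown separately as unconfirmed, so that patients who progress early are not moved to Other.
- Add to the same row that the patient does not qualify for No change, so that the table matches the best-response definition above it.
- Change the sentence below the table to the same rule. Altering only that sentence would leave the 21-day condition in the row.

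The cost is wording and programming; no new data are needed. Deterioration rates will be somewhat lower. In the enumeration, 4 of the 11 three-visit sequences and 8 of the 85 six-visit sequences now labelled Deterioration would move to Other. Under a strict two-consecutive-visit rule, 6 and 16 would move. The reduction from this fix is therefore smaller than the simulated contrast above.
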